We have found that soft pediatric toothbrushes are more easily maneuverable in the mouths of endotracheally intubated subjects and enables removal of plaque without disturbing oral tubes. Soft bristles reduce potential for trauma and bleeding, and in our previous studies were not associated with adverse effects such as damage to mucosa which can result from hard bristled toothbrushes. We considered use of an electric toothbrush, but selected the manual toothbrush for two primary reasons. First, electric toothbrushes have been associated with significantly increased risk of transient bacteremia compared to manual toothbrushes in healthy populations. Second, electric toothbrushes have been tested in two VAP trials, and outcomes were no better than trials in which manual toothbrushes were used (neither manual nor electric toothbrushes have been shown to reduce VAP risk). Furthermore, the additional cost of an electric toothbrush as a standard of care will hinder broad adoption of the study findings to clinical practice settings.

We have also chosen not to use disposable toothbrushes. We reason that requirement for a disposable toothbrush will reduce translation to practice related to increased cost. Further, we recently examined environmental contamination of toothbrushes in the ICU (F31NR012340, Fellow: [name]). While 14 of 100 toothbrushes became contaminated with potential pathogenic organisms over 24 to 72 hours of use, there was a significant association between tooth brush contamination and the use of a storage container ( $p$ -value = 0.01), regardless of whether the toothbrush was reused for 24, 48, or 72 hours. Thus, our intervention will include rinsing the toothbrush well after use, and storage in a dry well ventilated space apart from other patient care items (a condition in which none of the toothbrushes studied became contaminated).

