Specific Aim 2 is to quantify and compare the safety of three tooth brushing frequencies on serious adverse outcomes, including ventilator associated complications and clinically relevant healthcare-associated infections. For aim #2, a composite HAI endpoint will be constructed consisting of VAP, bacteremia, and sepsis. Since HAIs are anticipated to be rare events across the 3 tooth brushing regimens, no formal between-group statistical testing will be conducted. Instead, 95% confidence intervals will be calculated for the proportion of subjects with HAI in each treatment arm. In addition, using person days of observation (i.e. days since intubation), we will calculate incidence rates (IR) of HAI by treatment arm and then calculate the number needed to harm (NNH) using the single daily brushing regimen as the

reference group and the formulas:  $NNH_{21} = (1 / (IR_2 - IR_1))$  and  $NNH_{31} = (1 / (IR_3 - IR_1))$  where  $IR_n$  = observed incidence rate in each treatment arm. In the event that the formal test of non-inferiority fails for the single daily brushing regimen, we will define clinically-relevant “compromised” safety as an NNH of 100 per less. This would be interpreted as 100 individuals or less being treated with the multiple daily tooth brushing to develop an HAI that otherwise would not have occurred with the single daily brushing regimen.

Clinical recommendations defined *a priori* and developed from the analyses conducted for aims 1 and 2 will be developed as defined in Table 2.

Table 2. Application of study findings to tooth brushing frequency recommendations

Comparison Groups a	Non-Inferiority	NNH	Recommendation	Rationale
1 versus 3	Supported	N/A	1 time/day	1 time/day non-inferior and safe
1 versus 3	Not supported	$\geq 100$	3 times/day	1 time/day inferior, 3 times/day safe
1 versus 3	Not supported	$< 50$	1 time/day	1 time/day inferior, but 3 times/day safety concern
1 versus 3	Not supported	50 to 100	See 1 vs. 2	1 time/day inferior, but 3 times/day safety concern
1 versus 2 b	Supported	N/A	1 time/day	1 time/day non-inferior and safe
1 versus 2 b	Not supported	$\geq 100$	2 times/day	1 time/day inferior, 2 times/day safe
1 versus 2 b	Not supported	$< 100$	1 times/day	1 time/day inferior, but 2 times/day safety concern

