## **XII. DATA AND SAFETY MONITORING**

A Data and Safety Monitoring Plan (DSMP) will be implemented for the purpose of monitoring safety of the study, including but not limited to review of adverse events. Monthly DSMP meetings will include the PI, project director, biostatistician, data manager, and GRAs. The DSMP meetings will include review of all safety and adverse events data. Summary reports of data will be prepared by the data manager and project director. DSMP reports will consist of protocol compliance with inclusion/exclusion criteria, gender and minority and adverse events review. Written minutes of DSMB meetings with summaries of adverse events will be forwarded to the IRB and NIH as part of the annual reporting process. Research staff will report any adverse event immediately to the PI. Enrollment, study fidelity, and safety data will be reviewed regularly at study team monthly meetings. All adverse events will be reported to the TGH and USF IRBs, and the NIH, following institutional and NIH guidelines. We believe that the protocol is low risk and that this should be adequate.

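### Aim 2 compares arms on healthcare-associated infection alone, so Table 2 can call two or three brushings a day 'safe' although harms of the brushing session are neither named for collection nor compared by arm

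*Combined protocol and SAP*

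**What the plan says.** Section XI (Data Analysis Plan), Specific Aim 2, builds one safety endpoint: "a composite HAI endpoint will be constructed consisting of VAP, bacteremia, and sepsis". Because such infections are expected to be rare, "no formal between-group statistical testing will be conducted". Each arm gets a 95% confidence interval for the proportion infected and an incidence rate per person-day. The NNH is the reciprocal of the rate difference from once daily. Compromised safety is defined as "safety as an NNH of 100 per less", and the event counted is infection: the text speaks of people treated with "multiple daily tooth brushing to develop an HAI that otherwise would not have occurred with the single daily brushing regimen". The exploratory safety model under Specific Aim 3 also uses infections only.

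Table 2 converts the result into a recommendation. If non-inferiority fails and the NNH is 100 or more, the rationale for three times daily reads "1 time/day inferior, 3 times/day safe". The two-times-daily row is worded in the same way. Where once daily is non-inferior it is called safe with no NNH at all (N/A).

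Session hazards appear only in Section IX, Method, where the choice of brush is justified. The pediatric brush "enables removal of plaque without disturbing oral tubes", and "Soft bristles reduce potential for trauma and bleeding". The same paragraph says that soft brushes were not associated with effects such as mucosal damage in the team's earlier studies. A mouth prop may be used in some subjects.

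Table 1 lists SIRS, infection surveillance, length of stay and length of intubation as serious outcomes. It has no row for adverse events, bleeding, mucosal injury or tube events. Section XII is generic: "Research staff will report any adverse event immediately to the PI", with monthly review by the study team.

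**The concern.** The randomised factor is the number of brushing sessions. Any harm that arises from the session is therefore directly relevant to a comparison of frequencies, and Section VII (Innovation) says the analysis will weigh benefit against harm. Yet the safety half of the decision rule sees only infection. Monthly review under Section XII is monitoring, and it produces no estimate by arm.

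What is at stake is the breadth of the conclusion. A reader of the trial's recommendation would take 'safe' to mean that the main risks of brushing more often had been compared. The plan supports a narrower statement about infection. The gap starts at collection, because no document names the session events to be recorded, and it continues into the analysis.

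**Working it through.** **1. The plan's own safety figure.** Section XI (Statistical Power and Sample Size Justification) gives 0.01 to 0.13 as the 95% interval for an infection proportion of 0.05 with n = 69. With x = 0.05 × 69 = 3.45, the exact (Clopper-Pearson) interval is 0.012 to 0.131, so the figure reproduces. It concerns infection; no precision is given for any other harm.

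**2. Each possible harm against the plan.**

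| Harm | Named for collection | Analysed by arm | Enters Table 2 |
|---|---|---|---|
| VAP, bacteremia, sepsis | Yes (Table 1) | Yes (composite) | Yes (NNH) |
| Tube displacement, unplanned extubation | No | No | No |
| Oral bleeding, mucosal injury | No | No | No |
| Any other adverse event | Generic report to the PI | No | No |

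**3. Exposure.** One, two or three sessions a day for at most 7 days gives up to 7, 14 or 21 sessions.

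**4. Illustration.** The documents give no per-session risk, so q below is an assumption, taken as constant and equal in all arms. Risk over s sessions is 1 − (1 − q)^s, and cumulative NNH (3 versus 1) is 1 / (risk at three daily − risk at once daily). The plan's formula uses person-day rates. Those are about 3q and q per day, so NNH = 1/(2q).

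| Assumed q per session | 7-day risk, once | 7-day risk, three times | NNH, 7 days | NNH, 4 days | NNH, person-day formula |
|---|---|---|---|---|---|
| 0.0007 | 0.49% | 1.46% | 103 | 180 | 714 |
| 0.002 | 1.39% | 4.12% | 37 | 63 | 250 |
| 0.005 | 3.45% | 9.99% | 15 | 26 | 100 |

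For q = 0.002 over 7 days: 1 − 0.998^7 = 0.0139 and 1 − 0.998^21 = 0.0412. The difference is 0.0273, and 1/0.0273 is about 37. By the person-day formula, 1/(2 × 0.002) = 250.

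The two scales differ about sevenfold. Section XI gives a person-day formula but interprets the result as a number of individuals, so it does not settle which scale the cut-off of 100 belongs to.

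**5. What the earlier experience can exclude.** Section IX (Method) reports 229 subjects assigned to brushing three times daily. The documents give no event count. If it had been zero, the exact two-sided 95% upper limit would be 1 − 0.025^(1/229) = 1.6%. If that 1.6% were the risk over 21 sessions, q would be about 0.00077, the once-daily risk about 0.54%, the difference about 1.06% and the cumulative NNH about 94. In the other direction, with 3 days of brushing (9 sessions), q = 0.002 would imply about 4 affected subjects among 229 and q = 0.005 about 10. The higher values of q therefore fit poorly with the statement on mucosal damage.

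**6. What a by-arm table could show.** With 115 randomised per arm (345/3), zero events would give an upper 95% limit of 3.2%; with 69 it would be 5.2%. At 115 per arm over 7 days, two-sided 0.05, a test of 3 versus 1 has about 14% power at q = 0.001 and 51% at q = 0.005. That supports a descriptive table rather than a test.

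**The case against.** The case for leaving the plan alone has several parts.

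- Aim 2 is framed around serious adverse outcomes, and minor bleeding is not obviously one. Section XVI.E (Potential Risks) names aspiration and bloodstream translocation as the routes of harm, and the composite targets them.
- Compromised safety is explicitly defined through infection, so a careful reader could already read 'safe' that way.
- The remark about oral tubes concerns ease of handling and does not list a hazard.
- Soft brushes are reported as not associated with mucosal damage.
- Study staff are at the mouth up to three times as often in one arm as in another, so a by-arm table could show more bleeding through observation alone.

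Most of this stands, and it limits the point. It does not answer the central gap: the label in Table 2 is unqualified, and no comparison of any non-infectious harm is planned. The statement on soft brushes gives no counts, makes no comparison across frequencies and does not address tube events.

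Three stronger readings are tempting, and the documents do not support them. A reader might infer that session harms are already recorded and would sit unused; no document lists or defines them, so whether such data would exist is uncertain. A reader might infer that these harms rise with frequency; sessions do by design, but nothing says the harms do. A reader might infer that an unplanned extubation would be credited as benefit through a shorter intubation. Length of intubation is in Table 1, but Section XI gives it no comparison and Table 2 does not use it.

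**Conclusion.** The point holds in a limited form. The only safety quantity compared by arm is the infection composite. Table 2 labels two or three times daily 'safe' on its NNH alone, while session-related harms are neither named for collection nor compared. The defect is a conclusion broader than the analysis behind it; it is not evidence that any regimen is unsafe.

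Its size cannot be stated from the documents. The illustrative NNH values rest on an assumed constant per-session risk and on the scale chosen. Across the values shown they run from 15 to 714, so they cannot be read as showing that the plan's cut-off would be crossed. The change is still worth making, because it is cheap, leaves the sample size, the intervention and the primary analysis untouched, and makes the recommendation say what was measured.

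**What to change.** 1. On the existing adverse event form, name tube displacement or unplanned extubation, oral bleeding, and mucosal injury, to be recorded for all randomised subjects.
2. In Section XI, Specific Aim 2, add a descriptive table by arm: subjects with at least one such event, events per 1,000 delivered sessions, and the difference from once daily with a 95% confidence interval. Specify no formal test.
3. In Table 2, replace 'safe' with 'no HAI safety concern' and report the new table beside it.
4. State with the table that staff see the mouth more often in the higher-frequency arms, so ascertainment may differ.

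Cost: a few form fields, a count of delivered sessions for each subject, and one table. Few events are likely, so the intervals will be wide. The ascertainment difference can be disclosed but not removed by analysis.

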**Statistical Power and Sample Size Justification.** As described above, our primary aim is to evaluate whether a single daily tooth brushing regimen is clinically non-inferior (defined as an effect size of  $\leq 0.50$ ) to a regimen of brushing twice or 3 times daily. The test is considered one-sided as there is no known or postulated biological mechanism to expect a better clinical result (lower plaque score) with the once daily brushing regimen, while at the same time, no reason to expect a higher risk of serious adverse events with this regimen as compared to 3 times daily brushing. To be conservative, we assume that up to 40% of subjects enrolled will have missing data or not provide analyzable data due to intubation for less than 48 hours or less than 2 days follow-up measurement of dental plaque and mucosal inflammation after intubation; this is consistent with our previous and current projects. The non-inferiority trial is powered based on conventional guidelines of type I error rate ( $\alpha$ ) of 0.10 and 95% desired power, and specifying a 1-tailed tolerance limit for non-inferiority as an effect size of 0.50. With these conditions, a sample size of 69 subjects per group (i.e. testing group 1 versus 3) is required. This group size will also be sufficient if the non-inferiority test is not supported, and a secondary test of the 1 versus 2 times daily brushing regimens is necessary. For 3 groups, the required effective sample size is 207 (69 x 3 groups), which taking into account missing and non-usable outcome data results in a proposed total sample size of 345 subjects (i.e. 207 / 0.60). For specific aim #2, it is difficult to estimate the expected proportion of HAs to occur in the respective treatment arms, particularly given the recent change in Centers for Disease Control and Prevention (CDC) National Healthcare Safety Network (NHSN) surveillance definitions for ventilator associated complications, including VAP. If the proportion of subjects who experience HAI within one of the treatment groups ( $n=69$ ) is 0.05, the corresponding 95% confidence interval would be 0.01 to 0.13, indicating reasonable precision.

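### When non-inferiority is not supported, Table 2 picks the recommendation and safety label from an NNH point estimate, with no interval for the between-arm difference and cut-offs far inside its sampling error.

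*Combined protocol and SAP*

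**What the plan says.** All references are to Section XI, Data Analysis Plan.

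- **Inference planned for HAI (Specific Aim 2).** The aim is to quantify and compare safety. Because HAIs are expected to be rare, "no formal between-group statistical testing will be conducted". The only intervals planned describe each arm separately, as a proportion of subjects with an HAI. No interval is planned for the between-arm difference or for the NNH.
- **NNH formula.** The plan states: "using person days of observation (i.e. days since intubation), we will calculate incidence rates (IR) of HAI by treatment arm". NNH is the reciprocal of the difference between two such rates, with once daily as reference.
- **NNH interpretation.** The same paragraph reads the threshold per person: "100 individuals or less being treated with the multiple daily tooth brushing to develop an HAI".
- **When it is used.** "In the event that the formal test of non-inferiority fails for the single daily brushing regimen", an NNH of 100 or less counts as compromised safety. Table 2 shows NNH as not applicable when non-inferiority is supported.
- **What it decides.** For 1 versus 3 times daily, NNH of 100 or more leads to three times daily, labelled safe. NNH below 50 leads to once daily, with the rationale "1 time/day inferior, but 3 times/day safety concern". NNH of 50 to 100 sends the reader to the 1 versus 2 comparison, which has a single cut-off at 100.
- **Precision claimed (sample size paragraph).** For an HAI proportion of 0.05 with n=69, "the corresponding 95% confidence interval would be 0.01 to 0.13, indicating reasonable precision".

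**The concern.** Having too few events for a test is a reason for caution about the NNH. It is not a reason to act on its point estimate. Table 2 takes no account of sampling error, and the precision statement concerns one arm's proportion, whereas the decision rests on a difference between arms. If the cut-offs are small relative to the error of that difference, the pre-specified recommendation may be settled by a few infections and then reported as a safety finding. The error can go either way: a harmless regimen may be called a concern, or a harmful one called safe. The plan's Background and Innovation sections expect the result to change bedside practice quickly, so a wrong row matters.

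**Working it through.** **Inputs.** 69 evaluable subjects per arm; 345 enrolled, so 345/3 = 115 per arm at equal allocation; illustrative HAI risk 0.05; NNH cut-offs 50 and 100 (all Section XI). The plan calls the HAI proportion hard to estimate, so risks of 1% to 20% were also run. Mean days of observation are not stated. The intervention lasts at most 7 days, so 5 and 7 days per subject are assumed for the person-day scale.

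**Plan's own figures.** With one-sided alpha 0.10, power 95% and margin 0.50, n = 2(1.2816 + 1.6449)²/0.50² = 68.5, so 69 per group; 207/0.60 = 345. The exact (Clopper-Pearson) interval for 0.05 × 69 = 3.45 events is 0.012 to 0.131, matching the stated 0.01 to 0.13. Both reproduce.

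**Precision of the difference.** Half-width = 1.96 × √(2 × 0.05 × 0.95 / n):
- n = 69: 1.96 × 0.0371 = 0.073.
- n = 115: 1.96 × 0.0287 = 0.056.

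Per individual, the cut-offs are 1/100 = 0.01 and 1/50 = 0.02.

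**Per-individual scale: infections needed to change row** (NNH = n / excess infections).
- 69 per arm: 1 excess gives 69 (the 50 to 100 row); 2 give 34.5 (below 50).
- 115 per arm: 1 gives 115 (safe); 2 give 57.5 (50 to 100); 3 give 38.3 (below 50).

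**Per-individual scale: chance of a flag with no true difference.** Exact calculation from two independent binomials with equal risk. Zero or negative differences count as no concern; Table 2 has no row for them.

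| True risk, both arms | NNH ≤ 100, 115/arm | NNH ≤ 100, 69/arm |
|---|---|---|
| 1% | 15% | 31% |
| 2% | 23% | 37% |
| 5% | 32% | 42% |
| 10% | 37% | 44% |
| 20% | 40% | 46% |

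At 5% risk, NNH falls below 50 in 22% (115/arm) or 28% (69/arm). If risk truly doubles from 5% to 10%, 14% (115/arm) or 17% (69/arm) show no excess or an NNH above 100.

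**Person-day scale, as the formula is written.** The denominator becomes n × days. At 7 days, NNH of 100 or less needs 0.01 × 483 = 4.83, so 5 excess infections (69/arm), or 0.01 × 805 = 8.05, so 9 (115/arm). The threshold then corresponds to 0.01 × 7 = 7 points of absolute risk per subject, not 1.

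| Days per subject, n per arm | NNH ≤ 100 by chance (5% vs 5%) | True doubling (5% vs 10%) not flagged |
|---|---|---|
| 5 days, 69 | 8.3% | 51% |
| 5 days, 115 | 4.7% | 48% |
| 7 days, 69 | 3.9% | 64% |
| 7 days, 115 | 0.5% | 76% |

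**Effect of the gate.** With 69 per arm and a two-sided 95% interval, power for non-inferiority at zero true plaque difference is 83.6%, so NNH is consulted in about 16% of trials. Treating HAI as independent of plaque, the overall chance of a false NNH of 100 or less on the per-individual scale is 0.164 × 0.32 to 0.164 × 0.42, about 5% to 7%. If the true plaque effect equals the 0.50 margin, NNH is consulted in about 97.5% of trials and the figure is about 31% to 41%.

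**The case against.** Several objections carry weight.

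- **The gate.** A reader might infer that about a third of all such trials would raise a false safety concern. The documents do not support that. NNH counts only after non-inferiority fails, so the 32% and 42% are conditional on that failure; if plaque truly does not differ, the overall figure is about 5% to 7%.
- **The scale.** The written formula uses person-days, on which false flags are uncommon at 5 to 7 days. This stands, but it does not rescue the rule: the error moves to missed harm, and the formula no longer matches the per-individual meaning the plan gives it.
- **The 50 to 100 row.** A reader might also take every NNH of 100 or less as reversing the recommendation. For 1 versus 3 it does not, because that row leads to the 1 versus 2 comparison. Only NNH below 50 moves directly to once daily.
- **The 5% risk is illustrative.** True, hence the ranges above.
- **Other modelling.** Specific Aim 3 plans generalized estimating equations for safety, which could give a between-arm estimate with a standard error. They are exploratory, depend on enough events, and do not feed Table 2.
- **Estimation instead of testing is deliberate.** That is a legitimate choice, and it is the reason an interval for the difference is needed. It also argues against making a safety concern conditional on the interval excluding zero. With a Wald interval, such a rule would flag a true doubling from 5% to 10% in only about 22% (69/arm) or 31% (115/arm) of trials.

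**Conclusion.** The concern holds in conditional form. When non-inferiority is not supported, Table 2 rests the recommendation and the safety label on an NNH point estimate whose sampling error it ignores. On the per-individual reading, the half-width of the difference (5.6 or 7.3 points at 5% risk) is roughly three to seven times the 2-point and 1-point cut-offs, and false flags are frequent in the trials where NNH is consulted. On the person-day reading false flags are few, but about half to three quarters of trials with a true doubling go unflagged. The plan does not settle which scale applies, and neither gives a dependable label.

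The figures assume equal arms, at most one counted HAI per subject, the plan's illustrative 5% risk except where a range is shown, and 5 to 7 days of observation per subject on the person-day scale. The absence of a between-arm interval does not depend on any of these assumptions. The analysis plan should be changed; the point does not invalidate the trial.

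**What to change.** 1. Compute NNH on one scale that matches its per-individual interpretation, and say how a zero or negative difference is reported.
2. Report the between-arm HAI risk difference with its 95% confidence interval and the implied NNH interval, on all randomised subjects.
3. State in Table 2 that the safety label is inconclusive when that interval spans the cut-offs, instead of calling a regimen safe or a safety concern on the point estimate alone. Do not require the interval to exclude zero before a concern can be raised. What to recommend when safety is inconclusive is for the investigators to set in advance.
4. In the sample size paragraph, replace the claim of reasonable precision with the half-width of the between-arm difference: about 5.6 points (115 per arm) to 7.3 points (69 per arm) at 5% risk.

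The cost is analysis-plan and Table 2 wording, with no extra subjects or data. The downside is real: with intervals this wide, many results will be labelled inconclusive and the recommendation will be less decisive.
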